- HMPMA: 4-hydroxybut-2-ylmercapturic acid
- 2-HPMA: 2-Hydroxypropylmercapturic acid
- 3-HPMA: 3-Hydroxypropylmercapturic acid
- HR: Heart rate
- ITP: Investigational Tobacco Product
- ITR: Interactive Text Response
- ITRS: Interactive Text Response System
- NIDA: National Institute for Drug Abuse
- NMR: Nicotine metabolite ratio
- NNAL: 4-(Methylnitrosamino)-1-(3-pyridyl)-1-butanol
- NNN: *N*-Nitrosonornicotine
- PAH: Polycyclic aromatic hydrocarbons
- PheT: Phenanthrene tetraol
- PS-ECDI: Penn State Electronic Cigarette Dependence Index
- SAE: Serious adverse event
- SREC: Standardized Research E-cigarette
- TNE: Total Nicotine Equivalents
- VOC: Volatile organic compounds

PROTOCOL TITLE: Biomarkers in SREC Users

VERSION DATE: 03/13/2024

STUDY SUMMARY

| | |
|---|---|
| Study Title | Biomarkers of Exposure and Effect in SREC Users |
| Study Design | Within-subjects, repeated measures study |
| Primary Objective | Measure biomarkers of tobacco constituents and inflammation in smokers who will switch for six weeks to the Standardized Research E-cigarette (SREC) developed by the National Institute on Drug Abuse. |
| Secondary Objective(s) | Collect and analyze information on behavioral aspects and a comprehensive panel of subjective measures, including patterns and topography of SREC use. |
| Research Intervention(s)/Investigationa l Agents | Standard Research E-cigarette (SREC) developed by the National Institute on Drug Abuse |
| IND/IDE # (if applicable) | IU0000806, IU0000807, IU0000935, IU0000937, IU0000939/P00128 |
| Investigational Drug Services # (if applicable) | NA |
| Study Population | Cigarette smokers |
| Sample Size (number of abstinent completers) | 30 |
| Study Duration for Individual Participants | A total 11 weeks: 1 week baseline period, 6 weeks of assigned product use and a follow-up at week 10 |

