| WEEK | 92 | 91 | 0 | 1 | 2 | 3 | 4 | 6 | 10 |
| Visit window | | 1 week | | | Can be done anytime during the week | | | 1 day, + 3 days | -1 day, + 3 days |
| Biological samples and biomarker measures | | | | | | | | | |
| Alveolar carbon monoxide (CO) | | X | X | X | X | X | X | X | |
| Vital signs | | X | X | X | X | X | X | X | |
| Urine Pregnancy tests* | | X | | X | | | X | X | |
| NicCheck Test (if applicable) | | X | X | | | | | | |
| First morning void urine (for urinary biomarkers according to Aims 1-3) | | | X | | | | X | X | |
| Blood collection (morning, fasting)***** | | | X | | | | X | X | |
| Oral cells | | | X | | | | X | X | |
| Saliva | | | X | | | | X | X | |
| Subjective measures | | | | | | | | | |

PROTOCOL TITLE: Biomarkers in SREC Users

VERSION DATE: 03/13/2024

| | | | | | | | | | |
|--|---|---|---|---|---|---|---|---|---|
| Demographics Questionnaire | x | | | | | | | | |
| Tobacco Use History and Exposure | x | | | | | | | | |
| Nicotine Dependence (FTND)** | | | x | | | | | | |
| E-Cigarette Dependence (PS-ECDI) | | | | | | | | x | |
| Environmental Tobacco Smoke Exposure | | | x | | | | x | | |
| Occupational & Environmental Toxicants | | | x | | | | x | | |
| Brief Medical History | x | | | | | | | | |
| Concomitant Medications | x | | x | x | x | x | x | x | |
| Prime MD | x | | | | | | | | |
| CESD | x | | | | | | x | x | |
| Alcohol Use Questionnaire*** | x | | | | x | | | x | |
| Recreational Drug Use Questionnaire*** | x | | | | x | | | x | |
| Respiratory and Global Health | | | x | x | x | x | x | x | |
| Health Changes Questionnaire | | | x | x | x | x | x | x | x |
| Adverse Events Scale | | | x | x | x | x | x | x | x |
| ITR product use recording | | x | x | x | x | x | x | x | |
| Timeline Follow Back (TLFB)***** | | | x | x | x | x | x | x | |
| Product Evaluation Scale | | | x | x | x | | x | x | |
| Purchasing Task***** | | | x | | | | | x | |
| Drug Effects/Liking**** | | | x | x | x | x | x | x | |
| Tobacco Use Status | | | | | | | | | x |

* Pregnancy tests may also be administered at clinic visits if last menstruation reported being more than 35 days ago.

** All subjects will be evaluated at baseline.

*** Use over the past 30 days at weeks 2 and 6.

**** Regular cigarettes will be evaluated at baseline for all subjects; at the following visits only SREC will be evaluated.

***** To be done if participant reports using other tobacco products on the daily ITR or if there is missing data in the ITRS

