5.3 Study Duration

There will be approximately 11 weeks of participation for each subject (1-2 weeks between screening and the baseline period, 6 weeks of treatment, and 4 weeks follow-up). Over approximately 18 months, male and female smokers (N= up to 120) will be recruited for eligibility screening with the goal of 30 compliant completers (total abstinence for 6 weeks).

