17.2 Data Safety Monitoring

CTSI is responsible for periodically monitoring this study. While participating in the trial, AEs and concomitant medications will be assessed at every study visit and vital signs will be obtained periodically. AEs will typically be identified during the administration of the Health Changes Questionnaire and Respiratory and Global Health Questionnaire, and in some cases during the administration of the CES-D. Other events may be identified from physiological study measures or by spontaneous reports during assessments.

Assessment of Questionnaire Items

- Health Changes Questionnaire: If the participant answers 'YES' to Questions 1, 2, or 3, the interviewer will assess for an 'Adverse Event.'
 - 1) *Have you had any negative changes in your health since your last visit?*
 - 2) *Have you had any changes in medication since your last visit?*
 - 3) *Since your last visit, have you received any form of medical care?*
- Respiratory Health Questionnaire: If the participant indicates 'YES' to Question 6 regarding having a cold or flu the interviewer will administer the 'Adverse Event Log.'
 - 6) *In the past week, have you experienced any health problems, such as cold, flu, or other respiratory illness that would affect these respiratory symptoms?*
- CES-D: If the participant scores 16 or higher and are not already being monitored for depression, an 'Adverse Event' will be recorded and the licensed medical

professional will provide information regarding follow-up. If there is already an open event, information will be added to the existing 'Adverse Event.'

Assessment of Physiological Data

- **CO level:** An 'Adverse Event' will be recorded if the average of two consecutive measurements in the same visit is:
 - CO is greater than 50 ppm if CO at Baseline is < 20 ppm
 - CO is greater than 60 ppm if CO at Baseline is 20 – 34 ppm.
 - CO is greater than 70 ppm if CO at Baseline is 35 – 49 ppm.
 - CO is greater than 80 ppm if CO at Baseline is 50 – 64 ppm.
 - CO is greater than 90 ppm if CO at Baseline is 65 – 80 ppm.
- **Blood Pressure:**
 - The 'Adverse Event Log' and 'Blood Pressure and Heart Rate Symptom Checklist' will be completed if an automatic and subsequent manual blood pressure measurement during the same visit is at or above 160 systolic or 100 diastolic.

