 - The 'Adverse Event Log' and 'Blood Pressure and Heart Rate Symptom Checklist' will be completed if an automatic and subsequent manual blood pressure measurement during the same visit is below 90 systolic or 50 diastolic and the participant is experiencing symptoms listed on the 'Blood Pressure and Heart Rate Symptom Checklist.'
- **Heart Rate:**
 - The 'Adverse Event Log' and 'Blood Pressure and Heart Rate Symptom Checklist' will be completed if an automatic and subsequent manual heart rate measurement during the same visit is at or above 105 bpm.
 - The 'Adverse Event Log' and 'Blood Pressure and Heart Rate Symptom Checklist' will be completed if an automatic and subsequent manual heart rate measurement during the same visit is below 45 bpm and the participant is experiencing symptoms listed on the 'Blood Pressure and Heart Rate Symptom Checklist.'

Adverse Events Communicated by Participants

The occurrence of AEs will be sought by non-directive questioning of the participant at each visit during the study. AEs also may be detected when the participant volunteers them during or between visits or through physical examination, laboratory test, or other assessments.

Review and Reporting of Adverse Events and Serious Adverse Events

Co-Principal Investigators with oversight from [name]. (Medical Monitor) and [name] (Nurse Practitioner) will review all AEs and assess whether they are related to the study product.

PROTOCOL TITLE: Biomarkers in SREC Users

VERSION DATE: 03/13/2024

An AE is defined as the appearance or worsening of any undesirable sign, symptom, or medical condition occurring after starting the study procedures even if the event is not considered to be related to the study product. Medical conditions/diseases present before starting the study are only considered adverse events if they worsen after starting the study product. Abnormal laboratory values or test results constitute adverse events only if they induce clinical signs or symptoms, are considered clinically significant, or require therapy; there are no plans for active monitoring of laboratory tests as part of this project. Withdrawal symptoms are considered adverse event if the symptom had a significant impact on the participant's daily life, caused a major disruption of functioning, or took any medication for it.

To the extent possible, each adverse event will be evaluated to determine:

1. the severity grade (mild, moderate, severe)

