2. its relationship to the study product used (suspected/not suspected)
3. its duration (start and end dates or if continuing at final exam)
4. outcome (resolved/improved/unchanged/worsened; study product temporarily interrupted or permanently discontinued due to this adverse event; concomitant medication taken; non-drug therapy administered)
5. whether it constitutes a SAE

Information about all SAEs will be collected and recorded on the project's Serious Adverse Event Report Form. A SAE is defined an undesirable sign, symptom or medical condition which:

1. is fatal or life-threatening;
2. requires or prolongs hospitalization;
3. results in persistent or significant disability/incapacity;
4. constitutes a congenital anomaly or a birth defect;
5. is medically significant, in that it may jeopardize the subject and may require medical or surgical intervention to prevent one of the outcomes listed above.

Events not considered to be SAEs are hospitalizations that are:

1. elective or pre-planned, for a pre-existing condition that is unrelated to the products under study and did not worsen;
2. for general care, and/or overnight observation;
3. treatment on an emergency, outpatient basis for an event not fulfilling any of the definitions of serious given above and not resulting in hospital admission.

Safety evaluation will be performed on all accrued participants for whom SREC was dispensed. The assessment of safety will be based on the frequency of AEs and severity grade of AEs. Other safety data (e.g. CO, vital signs) will be considered as appropriate.

SAEs occurring after the participant has signed the consent form and until 4 weeks after the participant has stopped use of study product that are unexpected and at least possibly related will be reported. SAEs occurring more than 4 weeks after study discontinuation need only be reported if a relationship to study product is suspected. All AEs will be summarized by presenting, for each treatment group, the number and percentage of participants who experienced any AE, the number reporting AEs in each body system and

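### The adverse-event summary pools time before, on and after SREC, with no on-product window and no allowance for exposure time

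*Combined protocol and SAP*

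**What the plan says.** - **Start of the AE window.** Section 17.2 defines an AE as an undesirable event "occurring after starting the study procedures even if the event is not considered to be related to the study product". The starting point is study procedures, not first use of SREC.
- **Collection.** Table 3 in Section 5.2 has the row "Adverse Events Scale | | | x | x | x | x | x | x | x". Read against the column heads, this means Baseline 2, weeks 1, 2, 3, 4 and 6, and week 10. The Health Changes Questionnaire asks "Have you had any negative changes in your health since your last visit", so the Baseline 2 form looks back over the week since Baseline 1, when participants were still smoking. SREC is dispensed at Baseline 2.
- **Duration.** The Study Summary gives "A total 11 weeks: 1 week baseline period, 6 weeks of assigned product use and a follow-up at week 10". Section 5.3 gives "1-2 weeks between screening and the baseline period, 6 weeks of treatment, and 4 weeks follow-up".
- **Population and summary.** Safety is evaluated in everyone dispensed SREC, from the frequency and severity of AEs. All AEs are summarised as "the number and percentage of participants who experienced any AE", the number reporting AEs in each body system, and the number of AEs by type. This is to be shown by treatment group, although the study has one group. Severity and relatedness are listed, and AEs with a suspected link to the product are summarised separately.
- **Timing.** For each AE the plan records "its duration (start and end dates or if continuing at final exam").
- **Statistical section.** Section 15.1 says only that AEs and SAEs will be tabulated.
- **Early exits.** Sections 5.2 and 12.1 withdraw participants who have not stopped smoking within two weeks. Section 12.2 says data collection then stops.

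**The concern.** The safety question is what happens to people while they use SREC. As written, the AE frequency also counts events from the smoking week before dispensing and from the four weeks after supply ends. A reader cannot tell from the planned tables which events arose on the product.

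Three features of this trial make that matter. First, there is no control arm, so timing relative to SREC is one of the few aids to interpretation. Second, symptoms overlap across periods: Section 13.1 lists dizziness and nausea both as e-cigarette effects and as effects of returning to smoking after the study, so counts by type do not separate the periods. Third, follow-up is uneven by design. A completer contributes about six weeks on SREC and a participant withdrawn for continued smoking about two. A percentage with any AE therefore moves with the withdrawal rate even if the underlying AE rate is constant. Section 15.1 allows for non-compliance as high as 50%.

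**Working it through.** **1. The plan's own duration.** From the Study Summary: 1 (baseline) + 6 (product use) + 4 (week 6 to week 10) = 11 weeks, which matches the stated total. Section 5.3 gives 11 to 12 weeks (1-2 + 6 + 4).

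**2. Share of a completer's time off SREC.** Share = (pre-dispensing weeks + 4) / total weeks. This takes SREC use to end at week 6: the last envelopes cover weeks 4 to 6, and week 10 is a remote visit.
- From Baseline 1: 5/11 = 45%.
- Section 5.2 counts the calendar from a quit date about 3-5 days after assignment, which adds 0.43-0.71 week on SREC. The share becomes 5/11.43 = 44% to 5/11.71 = 43%.
- From dispensing: 4/10 = 40%, or 37-38% with the same extra days.

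**3. Effect on the any-AE percentage.** The documents give no AE rate, so the rates here are assumptions. Take a constant rate r per person-week, no SREC effect and equal ascertainment. Half of those dispensed complete (11 weeks observed, 6 on SREC) and half leave at week 2 (3 weeks observed, 2 on SREC).

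P(any AE in T weeks) = 1 − exp(−rT)

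At r = 0.1:
- Pooled: completer 1 − exp(−1.1) = 66.7%; early leaver 1 − exp(−0.3) = 25.9%; average 46.3%.
- On SREC: completer 1 − exp(−0.6) = 45.1%; early leaver 1 − exp(−0.2) = 18.1%; average 31.6%.

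| Assumed r per week | Pooled | On SREC | Gap (points) |
|---|---|---|---|
| 0.05 | (42.3 + 13.9)/2 = 28.1% | (25.9 + 9.5)/2 = 17.7% | 10 |
| 0.1 | 46.3% | 31.6% | 15 |
| 0.2 | (88.9 + 45.1)/2 = 67.0% | (69.9 + 33.0)/2 = 51.4% | 16 |

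**4. Lighter ascertainment after SREC.** Suppose at r = 0.1 that only half of the AEs in the four weeks after SREC are detected. A completer then has 1 + 6 + 2 = 9 effective weeks, giving 1 − exp(−0.9) = 59.3%, and the pooled figure is (59.3 + 25.9)/2 = 42.6%. If none are detected, there are 7 effective weeks, giving 1 − exp(−0.7) = 50.3% and (50.3 + 25.9)/2 = 38.1%. Against 31.6% on SREC, the gap is 11 and 6.5 points respectively.

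**5. What person-time does.** One completer and one early leaver give 11 + 3 = 14 person-weeks, of which 6 + 2 = 8 are on SREC. Under the assumptions in step 3 the expected rate is 0.1 per person-week in every period, whatever the withdrawal fraction. The percentage lacks this property: if everyone completed, it would be 67% pooled and 45% on SREC.

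**The case against.** The strongest reply is that 17.2 already provides more than one pooled figure. It plans counts by body system and type, listings of severity and relatedness, and a separate summary of suspected-related AEs. Every AE is assessed for its relationship to the product, and Section 3.4 makes within-person change in vital signs, CO and health questionnaires a safety endpoint. Conditions present before the study count only if they worsen after SREC starts, which is a partial on-product rule. Onset dates are recorded, so a split could be made at reporting. All of this is correct, and a reader should not infer that one percentage is the whole safety assessment or that data are missing. What remains is that none of the AE summaries is split by period, and that relatedness in an uncontrolled study is the investigators' judgment.

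A reader might also infer that AEs count from consent, so that half of 12 weeks is off SREC. The documents do not support this. The window that names consent, "SAEs occurring after the participant has signed the consent form and until 4 weeks after the participant has stopped use of study product", governs SAE reporting only, and Table 3 has no AE form at Screen or Baseline 1.

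It is also tempting to quote 67-70% pooled against 45% on SREC. That assumes everyone completes, which conflicts with a safety set of everyone dispensed and with withdrawal by week 2.

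Finally, week 10 is a single remote visit without vital signs, CO, CES-D or the Respiratory questionnaire, all of which can trigger an AE under 17.2. Five of the seven scheduled AE visits fall on SREC. This stands, and it shrinks the gap as step 4 shows.

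**Conclusion.** The point holds for the descriptive AE tables. Applied as written, 17.2 gives AE frequencies that mix the smoking baseline, SREC use and the period after SREC, and that ignore exposure time. About 43-45% of a completer's 11 weeks is off SREC, or about 40% from dispensing. Under the stated assumptions the pooled any-AE figure is about 46% against 32% on SREC at 0.1 AE per person-week. The gap is 10 to 16 points over assumed rates of 0.05 to 0.2. At 0.1 it falls to between 6.5 and 11 points if half or none of the AEs after week 6 are detected. These figures illustrate the mechanism and do not forecast the trial's AE rate.

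Two stronger conclusions should be avoided. The pre-dispensing week is not an adequate control: if 30 to 60 people are dispensed SREC (assumption), one week at 0.1 yields 3 to 6 events, collected at one visit. Nor does the gap bias any test, since the study has one arm and neither the primary biomarker analysis nor any stopping rule depends on this table. The change is worth making because safety is judged on AE frequency and the remedy is nearly free.

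**What to change.** Amend the AE summary in 17.2, with a matching line in 15.1:

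1. Assign each AE by its recorded onset date to pre-dispensing, on-SREC (from dispensing or first use, whichever is chosen and stated, to last use) or post-SREC. Daily product-use entries can supply the dates of use. Say how the 3-5 days between assignment and quit date, when participants may use both products, are classified.
2. For each period, tabulate participants at risk, person-weeks, number and percentage with any AE, and events per person-week, by severity. Show the body-system, type and suspected-related summaries by the same periods.
3. Base the SREC safety statement on the on-SREC rows. Show the pre-dispensing row descriptively, with a note that it covers about one week and one collection visit, and note that week 10 ascertainment is lighter.
4. Delete the reference to treatment groups, which does not fit a single-arm study.

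The cost is some wording and one extra descriptive table, with no new data. The split will not separate SREC effects from smoking withdrawal, because both fall in the on-SREC window; the text should say so.

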18.0 Provisions to Protect the Privacy Interests of Participants

18.1 Protecting Privacy

It will be made clear to participants that all information obtained during assessments is confidential and that no information will be shared with the participants' clinicians unless the participant requests this in writing. The only information that will be shared with clinicians upon such request by a participant would be clinical measures such as blood pressure or heart rate. Biomarkers analyzed for the study will not be shared.

While all the samples and information will be collected specifically to achieve the goals of this proposal, de-identified individual subject data and back-up samples may be made available to other researchers for research purposes after our study is complete. We will obtain permission from subjects to allow de-identified biosamples to be stored in a biorepository for future analyses of biomarkers or genotyping.

18.2 Access to Participants

There will be no access to medical records or any other sources of private information about the participating subjects.

19.0 Compensation for Research-Related Injury

19.1 Compensation for Research-Related Injury

The study poses minimal risk to participants. In the event that this research activity results in an injury, treatment will be available, including first aid, emergency treatment and follow-up care as needed. Care for such injuries will be billed in the ordinary manner, to the participant or the participant's insurance company. The participants will be asked to let the study physicians know right away if they think that they have suffered a research related injury.

19.2 Contract Language

Not applicable

20.0 Consent Process

20.1 Consent Process (when consent will be obtained)

The consenting process will take place remotely via a secured video-conferencing meeting invitation. Potential participants will be told the nature of the research during pre-screening and then at the screening visit. They will be told they may discontinue participation at any time and will not be discriminated against if they choose to do so. Interested subjects will be provided considerable time to review the consent form, consider whether or not to participate, and have any questions answered by the coordinator. Participants will be required to demonstrate an understanding of the study purpose and procedures prior to signing the consent form. Assessment of the subject's understanding will be completed via questions by a slideshow presentation. The consent form must be signed before the research is started. Immediately after signing, the participant will receive an email with a signed copy of the consent form.

The electronic consent forms will be stored in a REDCap database with restricted access for essential study personnel only. The electronic informed consent (eIC) will be built us the 'UMN e-Consent HRP-592-TEMPLATE-Biomedical'. The template will be customized to match the written informed consent form exactly. The electronic signatures obtain in the outline above are intended to be the equivalent of handwritten signatures. Therefore, the electronic signatures will occur in accordance with the predicated rule (e.g. approved, reviewed and verified) as outlined in the Food and Drug Administration's CFR part 11.

